## **11.5. Populations**

The two populations to be compared will be recipients of Mirasol-treated vs recipients of standard platelets.

## **11.6. Endpoints and Covariates**

The endpoint for the HLA alloimmunization study will be development at any post-transfusion time point of a positive HLA antibody test at the given assay cutoff in a subject who had a negative HLA antibody test at that assay cutoff at baseline (pre-transfusion).

A relevant covariate that will be analyzed in a secondary analysis is the number of platelet transfusions received prior to the alloimmunization event, which will allow calculation of the rate of alloimmunization per unit of platelets transfused.

## **11.7. Handling of Missing Values and Other Data Conventions**

Enrolled participants missing a baseline sample who do not have subsequent positive HLA antibody tests will be termed not alloimmunized. Participants missing a baseline sample who have subsequent positive HLA antibody tests will be termed unevaluable and will be excluded from analyses. Enrolled participants who have a baseline sample and have at least one subsequent post-transfusion sample will be used in the analysis.

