### **7.4.1. Dropouts and Missing Data**

Handling of subject dropouts and other forms of missing data with regard to the primary endpoint will be discussed in Section 8.1. Handling of subject dropouts and other forms of missing data with regard to key secondary endpoints is the responsibility of BSRI. No imputation of missing data will be applied to secondary, exploratory or safety endpoints unless otherwise specified.

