## 8.2. Secondary Endpoints

### 8.2.1. Key Secondary Endpoint

The Key Secondary Endpoint of HLA alloimmunization will be compared between the two groups using Fisher's exact test with a 2-sided test at the 0.05 level of significance. Blood System Research Institute will assume all analytic responsibilities of the Key Secondary Efficacy Endpoint for safety, interim and final analysis and details of this analysis are provided in Appendix II generated by BSRI.

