## **11.4. Analysis Objectives**

The objective of the study is to compare the rate of HLA alloimmunization for recipients of Mirasol-treated platelets and recipients of conventional platelets. The treatment effect will be measured by the odds ratio (OR). The relative odds of alloimmunization (comparing Mirasol-treated to conventional platelets) will be estimated at each of the three assay cutoffs, along with associated 95% confidence intervals. In addition, HLA antibody data will be examined using KM plots to explore time to alloimmunization, with the outcome of interest being time to development of new HLA antibodies. Individuals not experiencing alloimmunization will have their follow-up censored. All analyses will be conducted both as intention to treat analysis and a per protocol analysis.

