## **11.8. Statistical Procedures**

Odds ratios will be calculated to compare the risk of HLA alloimmunization in recipients of Mirasol-treated vs. conventional platelets. The exposure will be platelet type and the outcome will be development of a new HLA antibody. Development of HLA class I and HLA class II antibodies will be analyzed separately. The number of participants in each group at risk for alloimmunization will depend on the intention to treat and per protocol final categorization, but in general will be the number of participants who did not have detectable HLA antibodies at baseline at a given assay threshold.

In secondary analyses KM curves will be calculated using the longitudinal HLA antibody data to define subjects who are alloimmunized at baseline and the time to development of HLA alloantibodies post-transfusion. Development of HLA alloantibodies will be considered “failure” events during model specification, and the two arms of the study will be compared statistically using standard non-parametric tests, such as the log-rank test, with a p-value less than or equal to 0.05 considered evidence for significant difference

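### The HLA rule for missing baselines keeps subjects who test negative and drops those who test positive, which biases alloimmunization rates downward

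*SAP*

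**What the plan says.** HLA alloimmunization is the key secondary endpoint. SAP 8.2.1 compares the arms "using Fisher's exact test with a 2-sided test at the 0.05 level of significance", and 11.4 takes the odds ratio as the effect measure, estimated at three assay cutoffs. SAP 7.4.1 leaves missing data for this endpoint to the laboratory group: "Handling of subject dropouts and other forms of missing data with regard to key secondary endpoints is the responsibility of BSRI". The only rules given are the three sentences of 11.7:

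- No baseline sample, no later positive: "Enrolled participants missing a baseline sample who do not have subsequent positive HLA antibody tests will be termed not alloimmunized".
- No baseline sample, later positive: "Participants missing a baseline sample who have subsequent positive HLA antibody tests will be termed unevaluable and will be excluded from analyses".
- Baseline sample available: "Enrolled participants who have a baseline sample and have at least one subsequent post-transfusion sample will be used in the analysis".

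Section 11.6 counts an event only in a subject who tested negative before transfusion at the cutoff in question. Section 11.8 says the number at risk in general "will be the number of participants who did not have detectable HLA antibodies at baseline at a given assay threshold". No sensitivity analysis of the missing-baseline rule is planned. The file posted as the protocol carries the same text.

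**The concern.** Among subjects with no baseline sample, the post-transfusion result decides who is analysed: negatives enter the denominator and positives leave altogether. Excluding the positives is defensible, because their antibodies may predate the first study transfusion. Keeping the matching negatives is not, because it adds non-events from a group whose events have been removed.

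There is a second asymmetry. A subject with a baseline sample needs a later sample to be used. A subject without one need only lack a later positive, so someone never sampled at all would, read literally, count as not alloimmunized.

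The arm-level alloimmunization rates are directly affected. So are the HLA results reported to the DMC by treatment, age group and stratum (SAP 8.6), where cells are smaller. The same direction would carry into the Kaplan-Meier curves (11.8) and the per-transfusion risk (11.9) wherever the same subjects are used, since baseline-missing negatives contribute follow-up and transfusions but can never contribute an event.

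**Working it through.** **No stated figure to reproduce.** The documents give no expected alloimmunization rate, missing-baseline fraction, sample size or power for this endpoint. Both p and m below are assumptions, shown over a range.

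**Set-up.** Let p be the true risk of a new antibody among baseline-negative subjects, and m the fraction with no baseline sample, taken as independent of outcome. As proportions of the baseline-negative subjects in an arm:

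- Events counted, only from those with a baseline: (1-m)p
- Non-events counted, from both groups: (1-m)(1-p) + m(1-p) = 1-p
- Rate under the rule: (1-m)p / [(1-m)p + 1-p] = (1-m)p/(1-mp)
- Odds under the rule: (1-m)p/(1-p), which is the true odds times (1-m)

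**Rates under the rule:**

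| True p | m = 2% | m = 5% | m = 10% | m = 20% |
|---|---|---|---|---|
| 5% | 4.9% | 4.8% | 4.5% | 4.0% |
| 10% | 9.8% | 9.5% | 9.1% | 8.2% |
| 20% | 19.7% | 19.2% | 18.4% | 16.7% |
| 30% | 29.6% | 28.9% | 27.8% | 25.5% |

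For example, p = 20% and m = 10% give 0.18/0.98 = 18.4%. The relative shortfall is about 1.4 to 1.9% at m = 2%, 7 to 10% at m = 10%, and 15 to 19% at m = 20%.

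**In counts.** The planned 558 mITT subjects give about 279 per arm. Take all as baseline-negative, with p = 20% and m = 10%. Events counted are 279 × 0.9 × 0.2 ≈ 50. About 279 × 0.1 × 0.2 ≈ 6 positives are dropped and 279 × 0.1 × 0.8 ≈ 22 negatives are kept. About 273 subjects remain, and 50.2/273.4 = 18.4%.

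**Simulation check (2,000,000 subjects, p = 20%, m = 10%).** The rule gave 18.4% whether 0%, 10% or 20% of subjects were antibody-positive at baseline. Excluding every baseline-missing subject returned 20.0%. If a further 10% of subjects have no post-transfusion sample and the first sentence of 11.7 is applied literally, the rule gives 18.1% (with 10% baseline-positive).

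**Treatment comparison.** The odds ratio under the rule is the true odds ratio × (1-m_T)/(1-m_C).

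- Equal missingness: no change. True risks of 10% against 20% give 0.444 with or without the rule at m = 10% in both arms. The risk difference does shrink, from -10.0 to -9.3 percentage points.
- m_T = 5%, m_C = 15%: a true odds ratio of 1.00 becomes 0.95/0.85 = 1.12.
- m_T = 15%, m_C = 5%: it becomes 0.85/0.95 = 0.89.

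**The case against.** The strongest reply is that 11.7 need not put these subjects in the denominator. Its first sentence only assigns a label. The one sentence that says who is used requires a baseline sample and a later sample, and 11.6 and 11.8 both rest on a negative baseline. On that reading there is no bias. But the first sentence would then serve no purpose, and the plan would be labelling one group as non-events while expressly excluding the other for nothing. Inclusion is the natural reading, and if restriction was meant, the text still has to say so.

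Several limits do stand:

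- The effect measure is the odds ratio, which equal missingness leaves intact. The baseline sample precedes transfusion in a randomized trial, and nothing in the documents suggests arm-dependent loss. The 5% against 15% split is purely illustrative.
- If only a few percent of baselines are missing, the effect is small.
- Some excluded positives may have carried antibodies before transfusion, so not all of them are lost events.
- The appendix does not say outright that baseline-missing subjects enter the Kaplan-Meier and per-transfusion analyses, and no size was computed for those.
- SAP 7.4 treats secondary outcomes as supportive and exploratory, so no primary conclusion depends on this rule.

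**Conclusion.** The concern holds. As written, 11.7 selects baseline-missing subjects on the outcome and conflicts with the endpoint and at-risk definitions in 11.6 and 11.8. The arm-level rates are biased downward for any m and p between 0 and 1: for a true 20%, to 19.7% at 2% missing and 18.4% at 10%. The size rests on assumed values of p and m and on missingness unrelated to outcome. The direction relative to the alternatives does not rest on that assumption: whatever the mechanism, the rule gives a lower rate than either excluding all baseline-missing subjects or including all of them, provided both kinds occur. The odds ratio is biased only if missingness differs by arm. The rule should be corrected before the HLA analysis; it does not threaten the primary conclusion.

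**What to change.** In Appendix II:

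- Delete the first sentence of 11.7.
- State that the at-risk set at each cutoff consists of subjects with a baseline sample negative at that cutoff and at least one post-transfusion sample, and that all subjects without a baseline sample are outside it whatever their later results.
- Apply the same set to the odds ratios, the Kaplan-Meier curves and the per-transfusion risk.
- Report the number of missing baselines by arm, split by later positive, later negative and never sampled.
- Add a sensitivity analysis that includes the baseline-missing subjects with post-transfusion samples, both positive and negative. Label it as likely to overstate the rate, because it counts any pre-existing antibodies as new.

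The cost is a few sentences and some denominator. At 279 per arm and p = 20%, the negatives removed number about 4 per arm if 2% of baselines are missing (279 × 0.02 × 0.8), 22 if 10% are missing and 45 if 20% are missing. No event counted under the present rule is lost.

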## **11.8. Statistical Procedures**

Odds ratios will be calculated to compare the risk of HLA alloimmunization in recipients of Mirasol-treated vs. conventional platelets. The exposure will be platelet type and the outcome will be development of a new HLA antibody. Development of HLA class I and HLA class II antibodies will be analyzed separately. The number of participants in each group at risk for alloimmunization will depend on the intention to treat and per protocol final categorization, but in general will be the number of participants who did not have detectable HLA antibodies at baseline at a given assay threshold.

In secondary analyses KM curves will be calculated using the longitudinal HLA antibody data to define subjects who are alloimmunized at baseline and the time to development of HLA alloantibodies post-transfusion. Development of HLA alloantibodies will be considered “failure” events during model specification, and the two arms of the study will be compared statistically using standard non-parametric tests, such as the log-rank test, with a p-value less than or equal to 0.05 considered evidence for significant difference

## 11.9. Approaches to Adjust for Multiplicity, Confounders, Heterogeneity

We do not plan to adjust for other potential covariates, unless evidence from the trial data suggest an unexpected imbalance between potential confounding factors such as the number transfused platelets or other patient characteristics. It is possible that platelet transfusion exposure will affect alloimmunization risk. In a secondary analysis, the risk of alloimmunization per platelet transfusion received prior to the alloimmunization event will be calculated.

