11.9. Approaches to Adjust for Multiplicity, Confounders, Heterogeneity

We do not plan to adjust for other potential covariates, unless evidence from the trial data suggest an unexpected imbalance between potential confounding factors such as the number transfused platelets or other patient characteristics. It is possible that platelet transfusion exposure will affect alloimmunization risk. In a secondary analysis, the risk of alloimmunization per platelet transfusion received prior to the alloimmunization event will be calculated.

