#### Additional Secondary Endpoints:

1. Occurrence of World Health Organization (WHO)  $\geq$  grade 2 bleeding
2. Time to first day of WHO  $\geq$  grade 2 bleeding
3. Occurrence of WHO  $\geq$  grade 3 bleeding
4. Occurrence of PLT refractoriness defined as 2 sequential transfusion episodes, each with corrected count increments (CCIs)  $<$  5000 measured 1-hour post-transfusion
5. Occurrence of PLT refractoriness as defined above and with a positive antibody test within 14 days before or after the onset of PLT refractoriness
6. Number of PLT transfusion episodes per subject, i.e., frequency of transfusion
7. Days of PLT support; the number of days from the first to the last PLT transfusion
8. PLT utilization (average number of PLTs transfused)
9. CCIs at 1 hour and  $\geq$  18 but  $<$  30 hours post-PLT transfusion(s)
10. Total number of red blood cells (RBC) transfusions (number of units)/subject

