**6. Number of PLT transfusion episodes per subject, i.e., frequency of transfusion**

The analytic approach used to investigate secondary endpoint # 6 will be based on a negative binomial model. The total number of PLT transfusion episodes (regardless of whether or not the transfusion is determined to be “off-protocol”) will be calculated for each subject, and the negative binomial model will include only the covariate for treatment group which will give a regression coefficient; the exponentiated regression coefficient is an estimate of the ratio of the transfusion rate for the treatment groups. The offset in the negative binomial model will be the natural log of time in days from Day 0 to transfusion independence, study dropout or end of the 28-day treatment period for each subject.

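### Appendix II lets an observed imbalance in platelets transfused trigger adjustment of the HLA comparison, although that count arises after randomization and may be a mediator

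*SAP*

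**What the plan says.** The default in SAP 11.9 is an unadjusted analysis: "We do not plan to adjust for other potential covariates". The exception follows in the same sentence: "unless evidence from the trial data suggest an unexpected imbalance between potential confounding factors such as the number transfused platelets" or other patient characteristics. No size of imbalance, adjusted model or decision-maker is given. The next sentence adds: "It is possible that platelet transfusion exposure will affect alloimmunization risk". The Protocol file carries the same clause in its own 11.9 ("unless evidence from the trial data suggest an unexpected imbalance"); it is a copy and adds no separate evidence.

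Elsewhere the SAP treats platelet use as an outcome. The list of additional secondary endpoints in 6.3.2 has as item 6 "Number of PLT transfusion episodes per subject, i.e., frequency of transfusion". For that endpoint 8.2.2 fits a negative binomial model in which "the exponentiated regression coefficient is an estimate of the ratio of the transfusion rate for the treatment groups".

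For the HLA endpoint itself, 8.2.1 names Fisher's exact test, two-sided at 0.05, and 11.4 names the odds ratio, by intention to treat and per protocol. A separate secondary analysis in 11.6 uses "the number of platelet transfusions received prior to the alloimmunization event" to obtain a rate per unit transfused. Section 7.4 classes key secondary outcomes as supportive and exploratory.

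**The concern.** A confounder in a randomized comparison is a baseline factor that happens to be unbalanced. The number of platelets transfused during the trial is not one. If one product gives poorer increments or survives less well, its recipients may need more transfusions, and the imbalance is then a consequence of the product. If more exposure also raises the chance of an HLA antibody, the count lies on the path from treatment to outcome. Conditioning on it removes that part of the effect, whereas the intention-to-treat comparison in 11.4 is about the whole of it.

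The trigger adds a second problem, because the decision to adjust is taken after the imbalance is seen and under no stated rule. The appendix already produces 3 cutoffs x 2 antibody classes x 2 analysis populations = 12 odds ratios. Optional adjustment could turn these into 24, with nothing to say which is the main one.

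**Working it through.** **Setting the sections side by side**

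1. Treatment to count: 8.2.2, endpoint 6, estimates the arm ratio of transfusion rates as a result of the trial.
2. Count to outcome: 11.9 says exposure may affect alloimmunization risk.
3. Rule: 11.9 calls the same kind of count a confounder and permits adjustment if the arms differ.

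Steps 1 and 2 make the count a possible mediator; step 3 would condition on it. Neither link is shown to exist, but the plan allows for both.

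**Size**

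The documents give no HLA event rate, effect size or power, and no mean or dispersion for transfusion counts. There is no stated figure to reproduce, so everything below is an illustration on assumed inputs.

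- Count = 1 + a negative binomial with mean 4 and dispersion 0.6 in the control arm, so the control mean is 5; the MIRASOL mean is 5 x ratio, with ratio 1.0, 1.2 or 1.4.
- Log-odds of alloimmunization = -2.9 + ln(direct OR) x arm + g x count, with g = 0.05 or 0.10 per transfusion and direct OR 1.0, 0.7 or 1.4. Control risk comes out at about 7% to 9%.
- 2,000,000 simulated subjects per scenario. The first figure in each pair is the unadjusted (total-effect) OR; the second is the OR adjusted for the count.

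| Direct OR | Ratio | g = 0.05 | g = 0.10 |
|---|---|---|---|
| 1.0 | 1.0 | 0.996 / 1.007 | 0.996 / 1.008 |
| 1.0 | 1.2 | 1.047 / 0.992 | 1.136 / 1.003 |
| 1.0 | 1.4 | 1.135 / 1.007 | 1.281 / 0.993 |
| 0.7 | 1.0 | 0.695 / 0.698 | 0.708 / 0.709 |
| 0.7 | 1.2 | 0.744 / 0.703 | 0.801 / 0.706 |
| 0.7 | 1.4 | 0.788 / 0.701 | 0.918 / 0.685 |
| 1.4 | 1.0 | 1.418 / 1.425 | 1.387 / 1.398 |
| 1.4 | 1.2 | 1.479 / 1.400 | 1.567 / 1.379 |
| 1.4 | 1.4 | 1.578 / 1.419 | 1.778 / 1.405 |

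At ratio 1.0 the two agree within 0.012, which is simulation noise. Otherwise adjustment returns the direct OR and drops the rest. In the third row an increase in risk disappears. In the sixth row MIRASOL looks more protective than it is.

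**Direction.** Roughly, total OR = direct OR x exp(g x d), where d is the difference in mean count. With g = 0.10 and d = +2 (5 x 0.4), the factor is exp(0.20) = 1.22. The simulated 1.28 is larger because the spread of counts grows with the mean. With d = -2 the factor is exp(-0.20) = 0.82, and adjustment would then move the OR upward. This case was not simulated.

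**Trigger.** The plan gives no threshold. If it is taken as p < 0.05 for the difference in mean counts, with 279 per arm (558 / 2) and the same distribution, 4,000 replicates give an imbalance in 5% of trials at ratio 1.0, 33% at 1.1, 83% at 1.2 and over 99% at 1.4. The rule would act mostly when treatment has changed the count, which is when adjustment distorts the total effect.

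**The case against.** The strongest reply is that this is a conditional aside. The default is unadjusted, Fisher's exact test takes no covariate, and nothing says that an adjusted odds ratio would replace the specified one. That is right, and it limits the point. A reader might infer that harm through extra transfusions would be hidden; the documents do not support this. The two-by-two comparison still stands, and more transfusions in the MIRASOL arm would appear in endpoint 6. What remains is that 11.9 permits an invalid adjustment and leaves its status open.

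Three other stronger readings also fail.

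- A reader might object that the adjusting count stops at the event and so depends on event time. That cut-off is attached to the secondary per-transfusion analysis in 11.6 and 11.9, not to the conditional adjustment.
- A reader might cite endpoints 7 and 8 as well. Endpoint 7 is a duration. Endpoint 8, listed as "PLT utilization (average number of PLTs transfused"), is defined in 8.2.2 as platelets divided by units, which is average content and not amount of exposure. Endpoint 6 carries the argument.
- A reader might take one odds ratio from the table as the expected bias, or assume that it always runs toward 1. The inputs are assumed, and the direction depends on both links.

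The clause might also be read as meaning transfusions before the trial. It gives no time reference, but the sentences after it concern exposure before the alloimmunization event.

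Finally, the shift is modest against sampling error. With 279 per arm, all at risk, and 8% risk in each arm, SE(log OR) = sqrt(2 / (279 x 0.08 x 0.92)) = 0.31. The shifts in the table at ratios 1.2 and 1.4 run from ln(1.047/0.992) = 0.05 to ln(0.918/0.685) = 0.29, or about 0.2 to 0.9 of a standard error. This supports a lower severity. It does not make the adjustment valid.

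**Conclusion.** Wrong as written, with moderate to minor severity. Section 11.9 labels as a confounder a count that arises after randomization, that the SAP analyses as a treatment effect in endpoint 6, and that 11.9 says may influence the outcome. Adjusting for it after seeing an imbalance would bias the estimate of the total treatment effect, in either direction, if treatment changes the count and the count changes risk. If either link is absent, no mediated effect is lost. The size cannot be derived from the documents, and the figures above show only how the mechanism works under assumed inputs. The primary non-inferiority test is untouched, and the HLA endpoint is supportive and exploratory without multiplicity control (7.4, 7.4.4).

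**What to change.** In 11.9, delete the number of transfused platelets from the data-triggered adjustment. State instead that:

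- the unadjusted randomized comparison (Fisher's exact test and odds ratio) is the main HLA result;
- any covariate adjustment uses only baseline factors named in advance (the treatment-type stratum in 6.1 and the transfusion history in 7.11 are already recorded and could serve, but the choice is the sponsor's);
- any analysis using post-randomization transfusion counts, including the risk per transfusion already planned in 11.6 and 11.9, is supplementary and does not estimate the total treatment effect.

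The cost is a few sentences in Appendix II. No data collection, sample size or primary analysis changes, and no planned analysis is lost.
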